3. STATISTICAL METHODS

The statistical analysis will be performed using the R Statistical Software (Foundation for Statistical Computing, Vienna, Austria) version 3.6.0 or higher.

This is not a hypothesis testing study but an exploratory study with predefined precision of estimates for key efficacy and safety parameters; there are no formal statistical hypotheses tests to be tested, and there will be no adjustments for multiplicity of endpoints or within-subgroups comparisons.

Data will be summarized using appropriate descriptive statistics. Categorical data will be presented as frequencies and percentages. For continuous data, arithmetic mean, standard deviation (SD), median, interquartile range (IQR), minimum, and maximum will be presented. The 95% confidence interval of the observed proportions (calculated using either the Clopper-Pearson methodology, or the Poisson distribution, for frequencies below 10%) will be provided.

3.1 ANALYSIS POPULATIONS

The following populations will be considered for data analysis:

Effectiveness population

Effectiveness analysis population includes all patients who are enrolled and have received at least two cycles of Obinutuzumab.

Safety population

Safety analysis population includes all patients who are enrolled.

Screening failures are not considered for the analyses.

3.2 EFFECTIVENESS ANALYSIS

Effectiveness analysis population includes all patients who are enrolled and have received at least two cycles of Obinutuzumab.

In general, the time to endpoint will be defined as an interval between the date of enrolment (date of first visit) and date of first occurrence of the event. For patients who are event free, the censoring time will be calculated as a time interval between date of enrolment and the patient's final contact with available data concerning the event. The estimates and graphical presentation will be performed via Kaplan-Meier approach.

Logistic regression will be performed on the rate of endpoints in order to test the impact of covariates, i.e. age, sex, ECOG PS, Ann Arbor staging, FLIPI, hepatitis infection

(history of past/ resolved infection or latent HBV after prophylaxis as per standard treatment guidelines), chemotherapy backbone choice, medical history and history of FL, comorbidities.

Exploratory analysis between different medical treatments given or subgroup analysis will be performed using Cox regression model and including relevant covariates.

Corresponding 95% confidence intervals (CIs) will be provided for all statistical estimates.

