6.2 POPULATION

The patient population taking part in the study will comprise patients aged ≥ 18 years with untreated advanced FL.

Patients must meet the following criteria for study entry:

1. Signed Informed consent according to local regulations, after performing at least 2 cycles of induction treatment with Obinutuzumab and chemotherapy, within 1 year from beginning of treatment;
2. Age ≥ 18 years;

Patients who meet any of the following criteria will be excluded from study entry:

1. Any contraindications to Obinutuzumab therapy according to local label for specific indication;
2. Concomitant participation in an interventional clinical study;
3. Patients not receiving treatment for untreated follicular lymphoma with Obinutuzumab according to standard of care and in line with the current summary of product characteristics (SmPC)/local labeling

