- Time to response, defined as the time from first dose of Obinutuzumab to first documented response as assessed in clinical routine. Patients without response at the time of analysis and patients who are lost to follow-up will be censored at the date of their last tumour assessment. Patients without post-baseline tumor assessments will be censored at the time of their baseline visit unless death occurs prior to their first scheduled tumor assessment;

- Rate of patients with stable disease (SD);
- Effectiveness of Obinutuzumab in different patient subgroups, stratified by FLIPI (intermediate/high), ECOG-PS, age at study entry, hepatitis infection (history of past/resolved infection or latent HBV after prophylaxis as per standard treatment guidelines), chemotherapy backbone choice, presence of autoimmune disease, history of renal failure and liver failure;
- FDG-PET response at end of induction and end of maintenance, as per clinical practice. When PET is not performed, the alternative routine tumor assessment method will be collected.

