6.7.1 Effectiveness Analyses

Effectiveness analysis population includes all patients who are enrolled and have received at least two cycles of Obinutuzumab.

In general, the time to endpoint will be defined as an interval between the date of enrolment (date of first visit) and date of first occurrence of the event. For patients who are event free, the censoring time will be calculated as a time interval between date of enrolment and the patient's final contact with available data concerning the event. The estimates and graphical presentation will be performed via Kaplan-Meier approach.

Logistic regression will be performed on the rate of endpoints in order to test the impact of covariates, i.e. age, sex, ECOG PS, Ann Arbor staging, FLIPI, hepatitis infection (history of past/ resolved infection or latent HBV after prophylaxis as per standard treatment guidelines), chemotherapy backbone choice, medical history and history of FL, comorbidities. The list of the covariates to be included in the multivariate models will be detailed and justified in the statistical analysis plan document.

Exploratory analysis between different medical treatments given or subgroup analysis will be performed using Cox regression model and including relevant covariates. The list of the covariates to be included in the multivariate models will be detailed and justified in the statistical analysis plan document.

Further analyses will be performed to investigate different types of bias that might be present in this type of study design, e.g. time-dependent confounding, informative censoring, informative treatment changes/discontinuations, heterogeneity of results, and how to handle missing data.

Corresponding 95% confidence intervals (CIs) will be provided for all statistical estimates.

Primary endpoint

The primary endpoint is progression of disease at 2 years (POD24).

POD24 will be analyzed according to the survival analysis methods. The quartiles with their 95% confidence interval (estimated using Kaplan-Meier methods and Greenwood's formula) will be presented. Kaplan-Meier plots with a 95% CI will be prepared. Estimates for the survivor function will be obtained by the Kaplan-Meier approach.

Moreover, the POD24 will be analyzed as binary variable. Number and percentage of patients with its 95% confidence interval for POD24 will be calculated.

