2.3 PRIMARY OUTCOME MEASURES

Progression of disease at 2 years (POD24), defined as the time from the date of treatment initiation with Obinutuzumab until the first documented progression of disease

or death due to disease progression, whichever occurs first, within 24 months from the start of treatment with Obinutuzumab. Patients who have no disease progression and have not died due to disease progression or who are lost to follow-up at the time of analysis will be censored at the date of last tumor assessment where no progression was documented or the last date of follow-up for disease, whichever is last. Patients without post-baseline tumor assessments will be censored at the time of their baseline visit unless death due to disease progression occurs prior to their first scheduled tumor assessment. Patients who die for reasons not related to the disease progression within 24 months from the treatment start with Obinutuzumab will be excluded from the statistical analysis of the endpoint.

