2.4 SECONDARY OUTCOME MEASURES

2.4.1 Secondary Effectiveness Outcome Measures

- Progression free survival (PFS) at 2 and 3 years, defined as the time from the date of treatment initiation until the first documented progression of disease measured by routine clinical care or death from any cause, whichever occurs first. Patients who have no disease progression and have not died or who are lost to follow-up at the time of analysis will be censored at the date of last tumor assessment where no progression was documented or the last date of follow-up for disease, whichever is last. Patients without post-baseline tumor assessments will be censored at the time of their baseline visit unless death occurs prior to their first scheduled tumor assessment;
- Time to next treatment (TTNT), defined as the Time to initiation of subsequent systemic anti-cancer therapy following initiation of Obinutuzumab containing therapy. Patients not starting a subsequent systemic anti-cancer therapy will be censored at the date of the last study visit;
- Overall survival (OS), defined as the time from initiation of study treatment to death from any cause. Patients who still alive at the time of analysis and patients who are lost to follow-up will be censored at their last time known to be alive;
- Correlation between POD24 and OS;
- TTLCB, defined as the time from first dose to loss of clinical benefit as assessed by the treating physician (single or multiple reasons possible: e.g. disease progression, deterioration in ECOG PS, death, other). Patients who do not loss clinical benefit will be censored at the date of the last study visit. Patients without post-baseline tumor assessments will be censored at the time of their baseline visit unless death occurs prior to their first scheduled tumor assessment;
- Overall response rate (ORR);
- Complete response (CR);
- Complete response at 30 months (CR30);

- Duration of response (DoR) measured per clinical practice, defined as the time from first documentation of CR or partial response (PR) (whichever occurs first) until disease progression, as evaluated by the physician according to routine clinical practice or death. Patients who have no disease progression and have not died or who are lost to follow-up at the time of analysis will be censored at the date of last tumor assessment where no progression was documented or the last date of follow-up for disease, whichever is last;

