3.2.1 Primary Outcome Measures

The primary endpoint is progression of disease at 2 years (POD24).

POD24 will be analyzed according to the survival analysis methods. The quartiles with their 95% confidence interval (estimated using Kaplan-Meier methods and Greenwood's formula) will be presented. Kaplan-Meier plots with a 95% CI will be prepared. Estimates for the survivor function will be obtained by the Kaplan-Meier approach.

Moreover, the POD24 will be analyzed as binary variable. Number and percentage of patients with its 95% CI for POD24 will be calculated.

Logistic regression analysis will be performed to assess which variables are predictive of POD24. To identify factors associated with POD24, logistic regression analysis will be performed with backwards selection (removing factors with $P > 0.05$). Univariable associations between factors and POD24 will be calculated by using the Chi-square test.

In the analysis of POD24 will be excluded patients who die within 24 months from the treatment start with Obinutuzumab for reasons not related to the disease progression.

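### SAP 3.2 and Protocol 6.7.1 time endpoints in general from enrolment, the endpoint definitions start at first dose, and neither document says which rule prevails; the early-POD survival model adds a third origin, diagnosis.

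*SAP*

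**What the plan says.** **General rule.** SAP 3.2 states: "In general, the time to endpoint will be defined as an interval between the date of enrolment (date of first visit", running to the first occurrence of the event. Protocol 6.7.1 has the same sentence. For event-free patients, "the censoring time will be calculated as a time interval between date of enrolment and the patient's final contact". Both passages then refer to Kaplan-Meier estimation.

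**Endpoint definitions.** SAP 2.3 and 2.4.1 and Protocol 6.3.1 and 6.3.2 use a different origin. POD24 is "defined as the time from the date of treatment initiation with Obinutuzumab until the first documented progression of disease". "Overall survival (OS), defined as the time from initiation of study treatment to death from any cause" sets the start for OS. "Time to response, defined as the time from first dose of Obinutuzumab to first documented response as assessed in clinical routine" does so for response. PFS and TTNT also run from treatment initiation, and TTLCB runs from first dose. Duration of response starts at first documented response.

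**Analysis sections.** SAP 3.2.1 counts 24 months from treatment start, but only in the rule on unrelated deaths: "excluded patients who die within 24 months from the treatment start with Obinutuzumab". SAP 3.2.2 restates no origin for the Kaplan-Meier analyses. It does set one for the Cox model of early progression and OS: early progressors start at progression, and the others start two years after diagnosis. Protocol 6.7.1 says the same.

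**Enrolment.** Consent is signed "after performing at least 2 cycles of induction treatment with Obinutuzumab and chemotherapy, within 1 year from beginning of treatment" (Protocol 6.2). Protocol 6.4.2 equates enrolment with consent signature and places it after treatment has begun.

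**The concern.** The two origins cannot coincide for any patient, because enrolment is by design later than first dose. The sentence that tells a programmer how to compute event and censoring times matches none of the seven time-to-event endpoints, and nothing says that it yields to the definitions. Two analysts could both claim to follow the SAP and still produce different Kaplan-Meier curves from the same data.

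The Cox model has a separate fault. POD24 status is settled 24 months after treatment start, but patients without early POD start their survival clock two years after diagnosis. SAP 1.1 itself notes that patients without symptoms may be observed untreated for several years.

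**Working it through.** **1. The plan's own figures.** Exact Clopper-Pearson limits reproduce them. 39/300 (13%) gives 9.41 to 17.34, width 7.93 (stated 7.9). 240/300 (80%) gives 75.02 to 84.38, width 9.36 (stated 9.4). Both rest on binary rates, so the time origin does not enter.

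**2. The lag L between first dose and enrolment.** The documents give only bounds: two cycles to 12 months. Two cycles are about 1.5 to 2 months if 6 to 8 cycles fill the induction period of about 6 months (2 × 6/8 = 1.5; 2 × 6/6 = 2). The values L = 2, 6 and 12 below are assumptions.

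**3. Consequences of the enrolment clock that need no hazard model.**
- Time to response: a first response at month 3 in a patient enrolled at month 12 reads 3 − 12 = −9 months. A progression before enrolment is also negative.
- Reach: follow-up ends 42 months after first dose, so 42 − L months remain after enrolment: 40, 36 or 30. For L above 6 the patient cannot be observed to 36 months. Such a patient is censored, which costs precision and is not in itself a bias.
- Label: month 24 on the enrolment clock is month 26, 30 or 36 after first dose.

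**4. POD24 shift.** Take 13% at 24 months and a constant hazard h = −ln(0.87)/24. Among patients event-free at enrolment, with 24 months counted from enrolment, the risk is 1 − exp(−24h) = 13.0% at every L. The shift is zero.

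**5. PFS shift.** Let S(t) be piecewise exponential with a change at 24 months. The 24-month event risk among patients event-free at enrolment is 1 − S(24+L)/S(L). Two input pairs for PFS at 24 and 36 months are used: the protocol's 90%/80% (note to the sample-size tables), and 87%/80%, where 87% is set to agree with the 13% POD24.

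| L (months) | 90%/80% | 87%/80% |
|---|---|---|
| 0 | 10.0% | 13.0% |
| 2 | 11.0% | 13.2% |
| 6 | 12.9% | 13.6% |
| 12 | 15.7% | 14.2% |

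The largest shift is 15.7 − 10.0 = 5.7 points or 14.2 − 13.0 = 1.2 points. The difference comes from the ratio of the year-3 hazard to that of years 1 and 2:
- 90%/80%: [−ln(0.8/0.9)/12] / [−ln(0.9)/24] = 2.24
- 87%/80%: [−ln(0.8/0.87)/12] / [−ln(0.87)/24] = 1.20

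The protocol's 13% POD24 and 90% 24-month PFS cannot both hold in the same patients, because progression alone cannot exceed progression or death. Neither column is therefore the right one by default.

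**6. The Cox landmark.** Let g be the months from diagnosis to first dose. POD24 status is known at g + 24 months after diagnosis, but the clock starts at 24, which is g months too early. With g = 36 (an illustration), the clock starts 12 months before first dose and 36 months before status is known. If the exclusion of unrelated deaths within 24 months carries over to this model, a patient classified as free of early POD cannot have died in those g months, and the comparison favours that group.

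**7. OS from first dose without delayed entry.** Patients must be alive to consent. If all enrol at L and the hazard is k = −ln(OS36)/36, 36-month OS reads exp(−k(36 − L)). The documents give no OS figure. For an assumed true 90%, L = 12 gives 93.2%, and 93.2 − 90.0 = 3.2 points. The approximate 95% half-width at n = 300 is 3.4 points. For an assumed 94% or 97% the shift at L = 12 is 2.0 or 1.0 points, against half-widths of 2.7 and 1.9.

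**The case against.** The words *in general* mark a default, and the definitions are specific and agree between protocol and SAP. The primary objective is a proportion counted from start of therapy. An analyst who used the enrolment clock would meet negative times to response at once. The study is exploratory, with no hypothesis tests. All of this stands, and it makes the first-dose clock the likelier reading. It does not remove the defect, because a default that governs none of the listed endpoints should not stay in the methods section.

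A reader might infer stronger claims that the documents do not support.
- **That the wrong clock will be used.** The text is contradictory, but it does not show this.
- **That Kaplan-Meier POD24 would read 12.0%, 9.9% or 6.7% at lags of 2, 6 or 12 months instead of 13%.** These figures come from (0.13 − p)/(1 − p) with p = 1 − exp(−hL). They need an enrolment origin, all early progressors enrolled, their negative times dropped, and a window that still closes 24 months after first dose. Neither document states that combination. With lags uniform on 2 to 12 months the same formula gives 9.4%, but Kaplan-Meier reads about 12.0% if patients are censored when the window closes.
- **That many progressions precede enrolment.** The number is unknown. An exclusion criterion covers "Patients not receiving treatment for untreated follicular lymphoma with Obinutuzumab according to standard of care" and may keep out patients who have left first-line treatment, although Appendix 2 footnote a provides for enrolment after treatment completion.

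Survivor bias in OS is secondary on the figures in step 7. Both documents already list selection and the pooling of retrospective and prospective data as limitations. Protocol 6.7.1 promises bias analyses, although SAP 3.4 plans no sensitivity analyses.

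**Conclusion.** The contradiction is real, appears in both documents and is left unresolved. It should be fixed, but it does not threaten the primary proportion or the stated precision. Its numerical effect depends on hazard shape, enrolment lag and the handling of events before enrolment. The range runs from zero for POD24 (constant hazard, 24 months from enrolment) to 1.2 or 5.7 points for 24-month PFS at a 12-month lag, so no single figure should be headlined. The negative times and the limit on reaching 36 months follow from the design alone, but only if the enrolment rule is applied.

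The landmark at two years after diagnosis is a separate mismatch with POD24 as defined. It applies whichever clock is used for the other endpoints. Its size depends on the time from diagnosis to treatment, for which the documents give no distribution.

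**What to change.** 1. In SAP 3.2 and Protocol 6.7.1, replace the enrolment origin with: *Time zero is the first obinutuzumab dose for POD24, PFS, OS, TTNT, TTLCB and time to response; duration of response starts at first response; censoring times use the same clock and the censoring dates in the endpoint definitions.* State that retrospectively documented events count.
2. In SAP 3.2.2 and Protocol 6.7.1, start patients without early POD at 24 months from treatment start. Early progressors whose progression precedes enrolment enter the risk set at enrolment, because they had to survive to consent.
3. Optional: add a delayed-entry (left-truncated) sensitivity analysis for OS. Describe it as conditional on being alive at the earliest entry and as assuming that entry time is independent of survival.

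Items 1 and 2 cost one replaced passage and one changed landmark in each document, plus simple start-stop coding for early progressors. They adopt the sponsor's own endpoint definitions and leave the sample size unchanged. Item 3 needs a little more coding and gives wider intervals in the early months, when few patients are at risk.

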6.1.1 Overview of Study Design

A schedule of activities is provided in Appendix 2.

Figure 1 Study Scheme

Start Date of Study:

The study start date will be the date of the first data collection: the date from which information on the first study patient is recorded in the study database. The planned start date is July 2019.

End of Study:

The end of the study will be the date from which the last information of the last patient *still in the study* is recorded in the study database. The planned end date is December 2024.

The overall length of the study will be approximately 5 years.

This study will last 66 months. This period includes approximately 24 months of recruitment and 42 months after the last patient has started treatment with Obinutuzumab.

In addition, the Sponsor may decide to terminate the study at any time.

A data collection overview is provided in Appendix 2.

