2.6 DETERMINATION OF SAMPLE SIZE

Sample size of this clinical study is selected based on feasibility.

Sample size is justified for the primary effectiveness endpoint POD24 treated as binary variable. A sample size of 300 evaluable patients will allow estimation of the two-sided 95% confidence interval with a width equal to 7.9% (precision 3.95%) of the POD24 when the expected percentage is equal to 13%.

The Clopper-Pearson's formula has been used for the computation.

Moreover, a sample size of 300 evaluable patients will allow estimation of the two-sided 95% confidence interval with a width equal to 9.4% (precision 4.70%) of the PFS rate at 3 years (treated as binary variable) when the expected percentage is equal to 80%.

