3.8 INTERIM, FINAL ANALYSES AND TIMING OF ANALYSES

An interim analysis will be performed approximately one year after the first patient is included in the study in order to evaluate safety data (particularly, infections and events COVID related), demographic data (including potentially differences in patient enrolled pre- or post- COVID19 pandemic), FLIPI, treatment choices (obinutuzumab prescription profile and chemotherapy backbone choice per Italian region, per age range, per patient's profile and site dimension - outlying sites/ universities, etc.), impact of COVID19 over maintenance delay and treatment adherence.

A second interim analysis will be performed approximately two years after the first patient included in the study in order to evaluate safety and primary, and secondary effectiveness data (including POD24), and the impact of COVID-19 on the patients management.. Tables template for second interim analysis is reported in Appendix 3.

The final analysis will be performed at the end of the study.

4. **REFERENCES**

Armitage JO. Treatment of non-Hodgkin lymphoma. *N Engl J Med* 1993; 328(14):1023-30.

Cartron G, de Guibert S, Dilhuydy MS, et al. Obinutuzumab (GA101) in relapsed/refractory chronic lymphocytic leukemia: final data from the phase 1/2 GAUGUIN study. *Blood* 2014;124:2196–202.

Izutsu K. Treatment of follicular lymphoma. *J Clin Exp Hematop* 2014;54(1):31-7.

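### Covariates of POD24 are tested by logistic regression on event status with no rule for follow-up under 24 months; at the second interim this could produce spurious odds ratios for factors tied to enrolment date

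*SAP*

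**What the plan says.** SAP 2.3 defines POD24 as a time from first Obinutuzumab dose to progression or disease-related death within 24 months. Event-free patients are censored at the last assessment or follow-up. SAP 2.4.1 defines PFS, TTNT, OS and TTLCB as censored times too.

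For covariates, SAP 3.2 says "Logistic regression will be performed on the rate of endpoints in order to test the impact of covariates" and lists age, sex, ECOG PS, Ann Arbor stage, FLIPI, hepatitis infection, chemotherapy backbone, medical and lymphoma history, and comorbidities. SAP 3.2.1 adds: "Logistic regression analysis will be performed to assess which variables are predictive of POD24". Factors with P above 0.05 are removed backwards, and univariable associations use the chi-square test. Protocol 6.7.1 carries the same text. Cox regression is assigned to treatment and subgroup comparisons (SAP 3.2) and to predictors of OS (SAP 3.2.2).

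No section says how an event-free patient with under 24 months of follow-up is classified in binary POD24. SAP 3.6 has no missing-data handling and SAP 3.4 plans no sensitivity analyses, although Protocol 6.7.1 announces work on informative censoring and missing data.

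SAP 3.8 places the second interim about two years after the first inclusion, to evaluate "primary, and secondary effectiveness data (including POD24") among other data. On the study's 66 months, Protocol 6.1.1 says: "This period includes approximately 24 months of recruitment and 42 months after the last patient has started treatment with Obinutuzumab".

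**The concern.** Logistic regression and the chi-square test use whether an event was seen, not how long the patient was watched. This is harmless when everyone has been observed for the full 24 months. At the second interim they have not: patients enrolled in the first year have roughly twice the follow-up of those enrolled in the second.

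A covariate level that was commoner among early entrants would then show more events for that reason alone. Backbone choice is on the logistic list, and SAP 3.8 looks for possible differences between patients enrolled before and after the start of the pandemic, so a link between a covariate and enrolment date is plausible. At stake is whether factors reported as predictive of the primary endpoint reflect the disease or the calendar.

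**Working it through.** **The plan's own figure.** SAP 2.6 gives a 95% Clopper-Pearson width of 7.9% for POD24 of 13% with 300 evaluable patients. With 39/300 events the exact limits are 9.41% and 17.34%, width 7.93%. For "PFS rate at 3 years (treated as binary variable) when the expected percentage is equal to 80" per cent, 240/300 gives 75.02% to 84.38%, width 9.36% (stated 9.4%). Both agree. The documents give no odds ratio.

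**Inputs from the documents.** POD24 13% (11% and 17% are also in the Protocol 6.7.5 table); 3-year PFS 80%; 300 patients; recruitment about 24 months; second interim about month 24; consent after at least two cycles and within one year of first dose.

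**Assumptions not in the documents.** Even accrual; lag L from first dose to consent uniform on 1.5-12 months (1.5-4 and 8-12 also tried); constant hazard (Weibull shapes 0.8 and 1.3 also tried); no true covariate effect; event-free patients with short follow-up coded as non-events.

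**Step 1, follow-up.** A patient enrolled at month e has F = (24 − e) + L months from first dose at the interim. Mean L is 6.75. First-year entrants average 18 + 6.75 = 24.75 months; second-year entrants average 6 + 6.75 = 12.75.

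**Step 2, event shares.** For POD24, h = −ln(0.87)/24 = 0.0058 per month. The expected share is the mean of 1 − exp(−h·min(F, 24)): 12.2% for first-year and 7.1% for second-year entrants. Overall, naive POD24 would be (12.2 + 7.1)/2 ≈ 9.7% instead of 13%.

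**Step 3, odds ratio at full alignment.** (0.122/0.878)/(0.071/0.929) = 0.1390/0.0764 = 1.82.

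**Step 4, weaker alignment.** Let a share q of one level enrol in the first year, and the same share of the other level in the second. The observed shares are q·12.2 + (1 − q)·7.1 and (1 − q)·12.2 + q·7.1.

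| q | Shares | POD24 odds ratio | Range over lags, shapes and POD24 11-17% |
|---|---|---|---|
| 100% | 12.2% vs 7.1% | 1.82 | 1.40 to 3.09 |
| 80% | 11.2% vs 8.1% | 1.43 | 1.22 to 1.90 |
| 70% | 10.7% vs 8.6% | 1.27 | 1.14 to 1.53 |
| 60% | 10.2% vs 9.1% | 1.12 | 1.07 to 1.23 |

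**Step 5, untruncated PFS.** h = −ln(0.80)/36 = 0.0062. Shares are 14.2% and 7.6%; odds ratio 2.02 at full alignment.

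**Step 6, chance of a false finding.** With 150 patients per level and no true effect, a two-sided 5% chi-square test on POD24 rejects about 32% of the time at full alignment and about 15% at 80%.

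**Step 7, the complete-case alternative.** A first-year entrant has 24 months elapsed when L ≥ e, with probability mean(L)/12 = 6.75/12 = 56%; a second-year entrant never does. Overall that is 28%, about 84 of 300. With lag 1.5-4 it is (2.75/12)/2 ≈ 11%; with lag 8-12, (10/12)/2 ≈ 42%. At 13%, 84 patients yield about 11 events for backwards selection over the whole covariate list.

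**Step 8, final analysis.** Every patient has at least 42 months of potential follow-up, so both shares are 13% for POD24 and the odds ratio from staggered entry is 1.00. The same holds for PFS at 2 and 3 years.

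**The case against.** Several points on the other side stand.

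- A reader might infer that any factor linked to calendar time would show an odds ratio of about 2. The figures do not support that. About 2 needs untruncated PFS and a factor that coincides with enrolment year. For POD24 with a moderate link it is 1.1 to 1.3, and nothing in the documents suggests near-complete alignment for backbone or any other listed covariate.
- A reader might infer that the SAP schedules the covariate models at the second interim. SAP 3.8 says only that POD24 is evaluated then, and the Appendix 3 table templates cannot be seen here. It neither schedules nor excludes them.
- The bias depends on a coding the SAP does not state. Restricting to patients with 24 months elapsed gives a small sample, not a biased one.
- Region and site are not logistic covariates; they appear only in the descriptive prescription profile (SAP 3.5).
- Cox regression is already planned for subgroups, which include backbone, FLIPI, ECOG PS, age and hepatitis. But backbone is also on the logistic list, so one factor can receive two answers with no rule on which governs, and the factor search for POD24 is explicitly logistic.
- The primary objective is a proportion at 24 months and the study is declared exploratory. Logistic regression on a fully observed 24-month status is a legitimate analysis, so it need not be demoted at the final analysis.

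**Conclusion.** The point holds, conditionally. Covariates of a censored primary endpoint are tested on event status with no rule for incomplete follow-up, and no other section supplies one. If this is done at the second interim, the result is either a follow-up-driven bias or a model on a small part of the cohort, depending on a coding choice left open. The size of the bias rests on the assumed accrual, consent lag, event-time shape and strength of the link to enrolment date: substantial only for factors closely tied to that date, modest otherwise. The final analysis is free of bias from staggered entry, although early loss to follow-up that differs between covariate levels could still distort a model that counts those patients as non-events.

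**What to change.** In SAP 3.2 and 3.2.1 and Protocol 6.7.1:

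- Use Cox regression, with time measured from first dose, for covariate analyses of POD24, PFS and the other censored endpoints, as the SAP already does for OS and subgroups. For POD24, use the cause-specific hazard with follow-up truncated at 24 months.
- Keep logistic regression for the response rates.
- Run the POD24 logistic and chi-square analyses only at the final analysis, in patients with known 24-month status: progression or disease-related death within 24 months, or progression-free follow-up to 24 months.

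Cox regression uses each patient's observed time, so staggered entry alone produces no expected effect provided censoring is non-informative. The cost is SAP and protocol wording and slightly more standard R code. Effects are reported as hazard ratios instead of odds ratios. In the cause-specific model, deaths unrelated to progression are censored at death rather than excluded as in SAP 3.2.1, and the text should say so.
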